### 9.3 MISSING DATA

The nature of this trial is to assess the applicability of this model in the real world, so incomplete data that impacts the primary outcome will be assumed to be consistent with failure of therapy and drop-outs won't be replaced. However every effort will be made to obtain missing data and as the primary outcomes are not time point critical a wide latitude for admissibility of data will be employed. We will accept measures of SVR up to 12 weeks after the due SVR12 date.

### 9.4 TRANSFER OF DATA

No participant identifiable data will be transferred off site. Data will be stored, identified by trial number, with a separately held key to link trial number to identifiers that could be used for record linkage.

## 10 ADVERSE EVENTS

### 10.1 DEFINITIONS

An **adverse event** (AE) is any untoward medical event affecting a clinical trial participant. Each initial AE will be considered for severity, causality or expectedness and may be reclassified as a serious event or reaction based on prevailing circumstances.

An **adverse reaction** (AR) is where it is suspected that an AE has been caused by a reaction to a trial drug

A serious adverse event (SAE), serious adverse reaction (SAR) or suspected unexpected serious adverse reaction (SUSAR) is any AE, AR or UAR that at any dose:

- results in death
- is life threatening
- requires hospitalisation or prolongation of existing hospitalisation
- results in persistent or significant disability or incapacity
- is a congenital anomaly or birth defect
- Or is otherwise considered serious

### 10.2 RECORDING AND REPORTING AES AND SAES

All AEs and SAEs will be recorded from the time a participant consents to join the trial until the last trial visit. Participants with unresolved AEs at their last trial visit will be followed up until resolution or 30 days after their last trial visit whichever is sooner. SUSARS will be followed until resolution.

The CI or delegate will ask about the occurrence of AEs and hospitalisations at every trial visit. AEs will be recorded on the AE Log in the CRF. SAEs will be submitted on an SAE form to the Sponsor Pharmacovigilance Section ([[contact]](mailto:[contact])) within 24 hours of

becoming aware of the SAE except as described below and to MSD Global Safety group within 2 business days of the study team becoming aware of the event. SAEs will be assessed for expectedness and causality by the Investigator. The evaluation of expectedness will be made based on the knowledge of the reaction and the relevant product information (SmPC or IB). Refer to TASC SOP "Identifying, Recording and Reporting Adverse Events for CTIMPs". Causality will be assessed by the Sponsor

Hospitalisations for treatment planned prior to randomisation and hospitalisation for elective treatment of a pre-existing condition will not be considered as an SAE. However any adverse events occurring during such hospitalisation will be recorded.

Due to the large amount of comorbid disease and very high levels of illness and AEs that are expected to be present in this population, we will record as AEs/SAEs, but not report as SAEs to Sponsor Pharmacovigilance Section within 24 hours but will provide as line listings only to be included in the annual Development Safety Update Report (DSUR), in following the categories:

- Any death or hospitalisation for assault or accidental injury
- Hospitalisation for abscesses due to drugs use
- Hospitalisation for wound management due to drugs use
- Any death or hospitalisation due to infection
- Hospitalisation for elective or planned investigation or treatment
- Any death or hospitalisation for deteriorating renal function, high or low potassium levels
- Any hospitalisation due to nausea, vomiting, constipation or diarrhea

All other SAEs will be reported to Sponsor Pharmacovigilance Section within 24 hours and to MSD's Drug Surveillance Department within 2 business days of becoming aware of the event.

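### Protocol 10.2 sends serious infection, renal/potassium and gastrointestinal events to annual listings even if suspected to be drug related, and is not reconciled with the SUSAR deadlines in 10.3

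*Protocol*

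**What the plan says.** Section 10.2 sets a default: SAEs go on an SAE form to Sponsor Pharmacovigilance within 24 hours and to the manufacturer within 2 business days. The 24-hour rule carries an exception. Citing heavy comorbidity and expected background illness, the section lists seven categories that staff will record "but not report as SAEs to Sponsor Pharmacovigilance Section within 24 hours but will provide as line listings only", for the annual DSUR. Three of them read:

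- "Any death or hospitalisation due to infection"
- "Any death or hospitalisation for deteriorating renal function, high or low potassium levels"
- "Any hospitalisation due to nausea, vomiting, constipation or diarrhea"

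The other four are assault or accidental injury, abscesses, wound management, and elective or planned admissions. The section closes with "All other SAEs will be reported to Sponsor Pharmacovigilance Section within 24 hours", and the same sentence repeats the 2-business-day manufacturer route.

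On causality, 10.2 states "SAEs will be assessed for expectedness and causality by the Investigator" and, a little later, "Causality will be assessed by the Sponsor".

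Section 10.3 makes the Sponsor, together with the CI, responsible for reporting SUSARs: 7 days if fatal or life threatening, 15 days otherwise. Section 10.4 dates the DSUR to the anniversary of the Clinical Trial Authorisation.

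**The concern.** The reason given for the exemption is background illness. That supports lighter reporting of events unrelated to treatment. It does not support lighter reporting of events suspected to be reactions to the trial drugs, yet the three categories quoted above cover both. A listed event can also be a SUSAR, because under 10.1 a SUSAR is a serious event that is suspected to be caused by the drug and is unexpected.

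Staff then face two instructions for the same event: an annual listing under 10.2, and 7 or 15 days under 10.3. Meeting 10.3 depends on someone setting aside the explicit wording of 10.2.

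Three features of the trial make prompt sponsor review more important. Section 12.4 provides no independent data monitoring committee. Section 12.3 gives the steering committee's duties to the trial management group. Section 6.1.1 states that the genotype 3 combination is not licensed for that use. In addition, section 7.2 uses kidney function tests to judge whether participants can tolerate therapy, so the protocol itself treats renal function as a drug-safety matter.

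**Working it through.** The protocol gives no figure to reproduce. The check is a count and a comparison of the reporting times.

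**1. The seven categories in 10.2**

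| Category (paraphrased) | Includes deaths | Names a cause or plan outside the trial drugs | Condition on relation to trial drugs |
|---|---|---|---|
| Assault or accidental injury | yes | yes | none |
| Abscess | no | yes (drug use) | none |
| Wound management | no | yes (drug use) | none |
| Infection | yes | no | none |
| Elective or planned care | no | yes | none |
| Renal or potassium | yes | no | none |
| Gastrointestinal symptoms | no | no | none |

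Drug use is read here as illicit drug use. The contrast in drafting is plain: the abscess item, "Hospitalisation for abscesses due to drugs use", names its cause, while the infection item does not. Categories at issue: 7 − 4 = 3. Of those 3, 2 include deaths.

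**2. Times by route**

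| Route | Time | Section |
|---|---|---|
| SAE outside the list, to Sponsor | 24 hours | 10.2 |
| SUSAR, fatal or life threatening | 7 days | 10.3 |
| SUSAR, other | 15 days | 10.3 |
| Listed SAE, to Sponsor | next annual listing | 10.2, 10.4 |

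Suppose the listing is supplied only for the annual DSUR, since no other interval is stated. The wait then runs from near 0 to about 365 days, depending on when the event falls relative to the anniversary. At the upper end, 365/7 ≈ 52 times the 7-day limit and 365/15 ≈ 24 times the 15-day limit.

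**3. Does any text bring a suspected reaction back to the fast route?**

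- The exemption carries no condition on relatedness or expectedness.
- The closing sentence sends only the other SAEs by the 24-hour route, which confirms that listed events are outside it.
- The investigator assesses causality and expectedness, but nothing ties the result to the reporting route.
- The Sponsor also assesses causality, but cannot do so in time for an event it first sees in an annual listing.
- 10.3 neither refers to the list nor says that it overrides 10.2.

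**4. Manufacturer route**

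The exemption names only Sponsor Pharmacovigilance, which suggests that listed events still go to the manufacturer within 2 business days. The closing sentence applies both routes only to SAEs outside the list, which suggests that they do not. The text does not settle it.

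**The case against.** The best reply is that the two sections can be read together. Section 10.1 names SAEs, SARs and SUSARs separately, and 10.2 treats SUSARs separately when it says how long they are followed. The exemption mentions only AEs and SAEs. On this reading 10.2 relaxes routine SAE reporting and 10.3 governs SUSARs without exception. Listed events are still recorded and still assessed by the investigator, the CI shares the SUSAR duty, and the TASC SOP cited in 10.2 may set out escalation steps. A further point is that 10.3 sets deadlines only for unexpected reactions, so a fix covering every suspected reaction goes further than the conflict requires.

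Part of this stands. A careful reader could infer that 10.3 prevails, and escalation by another route is possible; for that reason 12 months is only an upper bound for one route. The reply does not remove the problem. A SUSAR is also an SAE, so it falls within the exemption as worded. The SOP is not shown, and the protocol's own wording would need correcting whatever the SOP says. Nor is the wider fix excessive: the Sponsor assesses causality and shares responsibility for SUSARs, so it needs suspected reactions promptly, before their final classification is settled.

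**Conclusion.** The concern holds. Section 10.2 states a reporting rule that, followed as written, defeats the deadlines in 10.3 for suspected drug-related events in three of the seven exempt categories, two of which include deaths. The listing route can take up to about 12 months, against 7 or 15 days.

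This rests on the listing being supplied only with the annual DSUR, and on no other route being used. The wording gap is certain; how often it would delay a report is not, because the documents give no event rate. The unclear manufacturer route is a smaller, separate ambiguity in the same section. This should be fixed.

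**What to change.** Amend section 10.2 as follows:

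- Limit the exemption to listed events that the investigator has assessed and documented as not suspected to be related to Zepatier or Sovaldi.
- State that any listed event with suspected relatedness goes to the Sponsor within 24 hours and to the manufacturer within 2 business days, so that 10.3 can be met, and cross-refer to 10.3.
- State whether the listed events that remain exempt go to the manufacturer.

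The cost is a protocol amendment, a documented relatedness check for listed events, and some additional expedited reports, whose number cannot be estimated from the documents. The relief that 10.2 seeks for background illness is kept.

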### **10.3 REGULATORY REPORTING REQUIREMENTS**

The Sponsor, together with the CI, is responsible for reporting SUSARs to the competent authority, the MHRA, the Research Ethics Committee (REC) and any other competent authorities. Fatal or life threatening SUSARs will be reported within 7 days and non-fatal and non-life threatening SUSARs within 15 days.

### **10.4 ANNUAL REPORTING REQUIREMENTS**

The following reports will be submitted each year as a condition of the authorisation to undertake a clinical trial or as a condition of a favourable opinion from a REC.

The DSUR will be prepared jointly by the Sponsor Pharmacovigilance Section and CI and submitted to the MHRA on the anniversary of date of Clinical Trial Authorisation (CTA).

An NRES CTIMP Safety Report Form will be sent to REC along with the DSUR. A NRES Annual Progress Report for CTIMPs will be prepared and submitted by the CI to REC, and copied to Sponsor, on the anniversary date of the REC favourable opinion.

Reports of SUSARs in the UK, urgent safety measures and any other safety reports submitted, for example, reports of a data monitoring committee, will also be accompanied by a Safety Report Form.

## 10.5 URGENT SAFETY MEASURES

The CI or other clinician may take appropriate immediate urgent safety measures in order to protect the participants of a CTIMP against any immediate hazard to their health or safety. The MHRA, REC and Sponsor will be notified in writing within three days.

## 11 PREGNANCY

Pregnancy is not considered an AE or SAE, however an abnormal outcome would be. If a pregnancy occurs, the CI or delegate must collect pregnancy information for female trial participants, who will be advised to stop trial medication immediately.

The CI or delegate should complete the TASC Pregnancy Notification Form and submit to the Sponsor Pharmacovigilance section within 14 days of being made aware of the pregnancy. Any pregnancy should be followed to outcome. Pregnancy follow up information must be recorded on the TASC Pregnancy Follow up form and submitted to the Sponsor Pharmacovigilance section.

### 11.1 CONTRACEPTIVE ADVICE TO PARTICIPANTS

All participants will be given contraceptive advice. With the aim of avoiding pregnancy during treatment. Avoiding getting pregnant by not having sex at all is obviously effective. If participants follow this strictly, no contraception is needed. If not, the following are effective types of contraception:

- Combined Oral Contraceptive Pill
- EVRA-oestrogen and progestogen: 'Transdermal Patch'
- Progestogen only pill: 'mini pill'
- Depoprovera injection (medroxyprogesterone acetate)
- Implanon Implant (Etonogestrel)
- Mirena Coil (Intra-Uterine System)
- IUD-copper containing intrauterine device
- Female sterilisation

- ‘Barrier methods’ such as the condom, diaphragm or cap, with or without spermicide, may also be used.

Male vasectomy is also a good form of contraception but only if the procedure has been confirmed afterwards by a physician to make sure it has worked. No contraception method is 100% reliable by itself. Even surgical sterilisation in men and women has been known to fail very occasionally therefore participants will be advised to use additional contraception from the start of the trial if they or their partner is of child bearing potential.

## **12 TRIAL MANAGEMENT AND OVERSIGHT ARRANGEMENTS**

### **12.1 TRIAL MANAGEMENT GROUP**

The trial will be co-ordinated by a Trial Management Group, who will meet regularly and co-opt co-investigators and the research nurses to the meeting as required.

### **12.2 TRIAL MANAGEMENT**

A Trial Manager will support the chief investigator (CI) in managing the trial, they will have the support of a trial Coordinator who will work closely with the research nurses. The research Nurses will oversee the trial and will be accountable to the CI.

A trial-specific Delegation of Responsibilities & Signature Log will be prepared for each Site, detailing the responsibilities of each member of staff working on the trial.

### **12.3 TRIAL STEERING COMMITTEE**

The trial management group (TMG) will carry out the duties of the trial steering committee.

### **12.4 DATA MONITORING COMMITTEE**

Since the drugs being used in this trial are licensed an independent Data Monitoring Committee will not be required.

### **12.5 INSPECTION OF RECORDS**

The CI will permit trial related monitoring, audits, REC review, and regulatory inspection(s). In the event of an audit, the CI will allow the Sponsor, representatives of the Sponsor or regulatory authorities direct access to all trial records and source documentation.

### **12.6 RISK ASSESSMENT**

A trial risk assessment was carried out by the Sponsor Research Governance Manager prior to Sponsorship approval being granted.

## **12.7 TRIAL MONITORING**

The Sponsor will determine the appropriate extent and nature of monitoring for the trial and will appoint appropriately qualified and trained monitors.

### **12.7.1 Potential Risks**

Potential adverse reactions to Zepatier and Sovaldi are as outlined in the SmPC. Having blood taken may cause some mild bruising.

### **12.7.2 Minimising Risk**

Participants will be monitored closely throughout the trial and adverse event monitoring will be undertaken as required. Every precaution will be taken to minimise discomfort whilst taking bloods, only trained and delegated members of staff will perform this procedure.

## **13 GOOD CLINICAL PRACTICE**

### **13.1 ETHICAL CONDUCT OF THE TRIAL**

The trial will be conducted in accordance with the principles of good clinical practice (GCP). In addition to Sponsorship approval, a favorable ethical opinion will be obtained from an appropriate REC. Authorisation from the MHRA and appropriate NHS R&D permissions will be obtained prior to commencement of the trial.

#### **13.1.1 Confidentiality**

All laboratory specimens, evaluation forms, reports, and other records will be identified in a manner designed to maintain participant confidentiality. All records will be kept in a secure storage area with limited access to trial staff only. Clinical information will not be released without the written permission of the participant, except as necessary for monitoring and auditing by the Sponsor, its designee or Regulatory Authorities. The CI and trial staff involved with this trial will not disclose or use for any purpose other than performance of the trial, any data, record, or other unpublished, confidential information disclosed to those individuals for the purpose of the trial. Prior written agreement from the Sponsor or its designee will be obtained for the disclosure of any said confidential information to other parties.

#### **13.1.2 Data Protection**

The CI and trial staff involved with this trial will comply with the requirements of the Data Protection Act 1998 with regard to the collection, storage, processing and disclosure of personal information and will uphold the Act's core principles. The CI and trial staff will also adhere, if appropriate, to the current version of the NHS Scotland Code of Practice on Protecting Patient

Confidentiality. Access to collated participant data will be restricted to the CI and appropriate trial staff.

Computers used to collate the data will have limited access measures via user names and passwords.

Published results will not contain any personal data that could allow identification of individual participants.

### **13.1.3 Insurance and Indemnity**

The University of Dundee and Tayside Health Board are Co-Sponsoring the trial.

**Insurance.** – The University of Dundee will obtain and hold Professional Negligence Clinical Trials Insurance cover for legal liabilities arising from the trial.

Tayside Health Board will maintain its membership of the Clinical Negligence and Other Risks Insurance Scheme (“CNORIS”) which covers the legal liability of Tayside in relation to the trial.

Where the trial involves University of Dundee staff undertaking clinical research on NHS patients, such staff will hold honorary contracts with Tayside Health Board which means they will have cover under Tayside’s membership of the CNORIS scheme.

**Indemnity.** Co-Sponsors do not provide trial participants with indemnity in relation to participation in the Trial but have insurance for legal liability as described above.

## **14 TRIAL CONDUCT RESPONSIBILITIES**

### **14.1 PROTOCOL AMENDMENTS**

The CI will seek Sponsor approval for any amendments to the Protocol or other trial documents. Amendments to the protocol or other trial docs will not be implemented without approval from the Sponsor and subsequent approval from the appropriate REC and/or MHRA, as appropriate, and NHS R&D Office.

### **14.2 PROTOCOL DEVIATIONS, BREACHES AND WAIVERS**

The CI will not implement any deviation from the protocol without agreement from the Sponsor, except where necessary to eliminate an immediate hazard to trial participants. In the event that the CI needs to deviate from the protocol, the nature of and reasons for the deviation will be recorded in the CRF, documented in a TASC Deviation & Breach Log and notified to the Sponsor. If this necessitates a subsequent protocol amendment, this will be submitted to the Sponsor for approval and then to the appropriate REC, Regulatory Authority and local NHS

R&D for review and approvals as appropriate. It is Sponsor policy that waivers to the Protocol will not be approved.

In the event that a serious breach of the protocol or GCP is suspected, this will be reported to the Sponsor immediately using the form “Notification to Sponsor of Potential Serious Breach or Serious Deviation”.

### **14.3 TRIAL RECORD RETENTION**

Archiving of trial documents will be carried out as specified in TASC SOPs (unless otherwise agreed with the Sponsor and by contract). As the data from this trial does not form part of an application for a Marketing Authorisation (MA) all trial documentation will be kept for at least 5 years.

### **14.4 END OF TRIAL**

The end of trial is defined as datalock. The Sponsor and CI have the right at any time to terminate the trial for clinical or administrative reasons.

The end of the trial will be reported to the Sponsor, REC, MHRA and NHS R&D Office within 90 days, or 15 days if the trial is terminated prematurely. The CI will ensure that any appropriate follow up is arranged for all participants.

A final report of the trial will be provided to the Sponsor, REC and MHRA within 1 year of the end of the trial.

### **14.5 CONTINUATION OF DRUG FOLLOWING THE END OF TRIAL**

This is not appropriate as the drugs being issued are only to be taken for 12 weeks during the trial.

## **15 REPORTING, PUBLICATIONS AND NOTIFICATION OF RESULTS**

### **15.1 AUTHORSHIP POLICY**

Ownership of the data arising from this trial resides with the trial team and their respective employers. On completion of the trial, the trial data will be analysed and tabulated, and a clinical trial report will be prepared.

### **15.2 PUBLICATION**

The clinical trial report will be used for publication and presentation at scientific meetings. Investigators have the right to publish orally or in writing the results of the trial. Summaries of

results will also be made available to Investigators for dissemination within their clinical areas (where appropriate and according to their discretion).

The clinical trial report will be used for publication and presentation at scientific meetings. Investigators have the right to publish orally or in writing the results of the trial. The International Committee of Medical Journal Editors recommendation on Authorship and Contributor-ship will be adhered to when presenting papers for publication or acknowledging public responsibility for appropriate portions of the content.

Abstracts will be presented at European Association for the Study of the Liver and American Association for the Study of Liver Diseases annual meetings, 4 papers are anticipated and target journals include Hepatology, J Hepatology and Gut, within 3 years of trial start.

The clinical trial report will be used for publication and presentation at scientific meetings. Trial investigators have the right to publish orally or in writing the results of the trial.

Summaries of results will also be made available to Investigators for dissemination within their clinical areas (where appropriate and according to their discretion).

